6.5 Safety

Evaluation of all AEs and SAEs including injection site reactions, ECGs, physical examination, vital signs and laboratory assessments, Assessment of anti-secukinumab antibody development (immunogenicity).

All blood draws and safety assessments should be done prior to study treatment administration. Appropriate safety assessments (e.g. evaluation of AEs and SAEs including injection site reactions) should be repeated after the dose is administered.

- Evaluation of AE/ SAE's
- Physical examination
- Vital signs
- Height and weight
- QuantiFERON TB-Gold test or PPD skin test
- Electrocardiogram
- Local tolerability (Injection site reactions)
- Laboratory evaluations (Hematology, Clinical Chemistry, LFTs, Urinalysis)
- Pregnancy and assessment of fertility
- Tolerability of secukinumab

6.5.1 Physical examination

A complete physical examination will be performed by a professionally trained physician or health professional licensed to perform physical examinations and listed on FDA Form 1572, at the scheduled study visits as indicated in [Table 6-1](#).

The physical examination will include the examination of general appearance, skin, neck, eyes, ears, nose, throat, lungs, heart, abdomen, back, lymph nodes, extremities, vascular and neurological system.

Information for all physical examinations must be included in the source documentation at the study site. Significant findings that are present before signing the ICF must be included in the relevant medical history eCRF. Significant findings made after signing the ICF which meet the definition of an AE must be recorded in the Adverse Event eCRF.

6.5.2 Vital signs

Vital signs include BP and pulse rate measurements. After the subject has been sitting for five minutes, with back supported and both feet placed on the floor, systolic and diastolic blood pressure will be measured using a validated device with an appropriately sized cuff.

If possible, vital signs assessments should be performed by the same study site staff member using the same validated device throughout the study.

Clinically notable vital signs are defined in [Appendix 1](#).

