 - Total abstinence (when this is in line with the preferred and usual lifestyle of the subject. Periodic abstinence (e.g., calendar, ovulation, symptothermal, post-ovulation methods) and withdrawal are not acceptable methods of contraception
 - Female sterilization (have had surgical bilateral oophorectomy with or without hysterectomy) or tubal ligation at least six weeks before taking study treatment. In case of oophorectomy alone, only when the reproductive status of the woman has been confirmed by follow up hormone level assessment

- Male sterilization (at least 6 months prior to screening). For female patients on the study, the vasectomized male partner should be the sole partner for that subject
 - Barrier methods of contraception: Condom or Occlusive cap (diaphragm or cervical/vault caps) with spermicidal foam/gel/film/cream/ vaginal suppository
 - Use of oral, injected or implanted hormonal methods of contraception or other forms of hormonal contraception that have comparable efficacy (failure rate <1%), for example hormone vaginal ring or transdermal hormone contraception. In case of use of oral contraception women should have been stable on the same pill for a minimum of 3 months before taking study treatment.
 - Placement of an intrauterine device (IUD) or intrauterine system (IUS)
 - NOTE: Women are considered post-menopausal and not of child bearing potential if they have had 12 months of natural (spontaneous) amenorrhea with an appropriate clinical profile (e.g. age appropriate, history of vasomotor symptoms) or six months of spontaneous amenorrhea as defined by Central Lab FSH and/or estradiol levels
12. Active ongoing inflammatory diseases other than PsA that might confound the evaluation of the benefit of secukinumab therapy
 13. Underlying metabolic, hematologic, renal, hepatic, pulmonary, neurologic, endocrine, cardiac, infectious or gastrointestinal conditions which in the opinion of the investigator immunocompromises the patient and/or places the patient at unacceptable risk for participation in an immunomodulatory therapy
 14. Significant medical problems or diseases, including but not limited to the following: uncontrolled hypertension ($\geq 160/95$ mmHg), congestive heart failure [New York Heart Association status of class III or IV], uncontrolled diabetes

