12.1 Appendix 1: Clinically notable laboratory values and vital signs

The following criteria will be used to define expanded limits and notable abnormalities of key laboratory tests. Whether or not any action needs to be taken to address notable laboratory or vital signs values will be determined by the investigator/qualified site staff, taking into

account the overall status of the subject. No specific action is pre-defined within this study protocol.

Liver function and related variables

ALT (SGPT)	> 3 x Upper Limit of Normal (ULN)
AST (SGOT)	> 3 x ULN
Total bilirubin	> 1.5 x ULN
Alkaline phosphatase	> 2 x ULN

Renal function and electrolyte variables

Creatinine (serum)	> 1.5 x ULN
--------------------	-------------

Hematology values

Hemoglobin	≥ 2.0 g/dL decrease from baseline
Platelet count	< Lower Limit of Normal (LLN)
White blood cell	< 0.8 x LLN
Neutrophils	< 0.9 x LLN
Eosinophils	> 1.1 x ULN
Lymphocytes	> 1.1 x ULN

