Decreased Lymphocyte	<lln -="" 1.5="" 10e9="" l<="" td="" x=""><1.5 - 1.0 x 10e9 /L	<1.0 - 0.5 x 10e9 /L	<0.5 x 10e9 /L	</lln>	<1.5 - 1.0 x 10e9 /L	<1.0 - 0.5 x 10e9 /L	<0.5 x 10e9 /L
count Decreased	<lln -="" 0.8="" 10e9="" l<="" td="" x=""><0.8 - 0.5 x 10e9 /L	<0.5 - 0.2 x 10e9 /L	<0.2 x 10e9 /L	</lln>	<0.8 - 0.5 x 10e9 /L	<0.5 - 0.2 x 10e9 /L	<0.2 x 10e9 /L
Creatinine increased*	>1 - 1.5 x baseline; >ULN - 1.5 x ULN	>1.5 - 3.0 x baseline; >1.5 - 3.0 xULN	>3.0 baseline; >3.0 - 6.0 x ULN	>6.0 x ULN
TBL increased	>ULN - 1.5 x ULN	>1.5 - 3.0 x ULN	>3.0 - 10.0 x ULN	>10.0 x ULN
GGT increased	>ULN - 2.5 x ULN	>2.5 - 5.0 x ULN	>5.0 - 20.0 x ULN	>20.0 x ULN
ALT increased	>ULN - 3.0 x ULN	>3.0 - 5.0 x ULN	>5.0 - 20.0 x ULN	>20.0 x ULN
AST increased	>ULN - 3.0 x ULN	>3.0 - 5.0 x ULN	>5.0 - 20.0 x ULN	>20.0 x ULN
ALP increased	>ULN - 2.5 x ULN	>2.5 - 5.0 x ULN	>5.0 - 20.0 x ULN	>20.0 x ULN

Table 2.8-2CTCAE grades for laboratory variables to be analyzed

Glucose increased				
(Hyperglycemia				
)	>ULN - 8.9 mmol/L	>8.9 - 13.9 mmol/L	>13.9 - 27.8 mmol/L	>27.8 mmol/L
Glucose				
decreased				
(Hypoglycemia)	<lln -="" 3.0="" l<="" mmol="" td=""><3.0 - 2.2 mmol/L	<2.2 - 1.7 mmol/L	<1.7 mmol/L	</lln>	<3.0 - 2.2 mmol/L	<2.2 - 1.7 mmol/L	<1.7 mmol/L
		>7.75 - 10.34		
Cholesterol high	>ULN - 7.75 mmol/L	mmol/L	>10.34 - 12.92 mmol/L	>12.92 mmol/L
Hypertriglycerid				
emia	1.71 - 3.42 mmol/L	>3.42 - 5.7mmol/L	>5.7 - 11.4 mmol/L	>11.4 mmol/L
*NT-4 C		1	1	

*Note: for "creatinine increased" the baseline criteria do not apply

Shift tables will be presented comparing baseline laboratory result (CTCAE grade) with the worst results (expressed in CTCAE grade) during the treatment phase (either initial or entire) analyzed. Of note, baseline will be defined as last assessment prior to first dosing in initial treatment phase. Patients with abnormal laboratory values will be listed and values outside the normal ranges will be flagged.

Newly occurring or worsening liver enzyme abnormalities will also be summarized based on the event criteria given in Table 2.8-3 below:

Parameter	Criterion
ALT	>3xULN; >5xULN; >8xULN;>10xULN, >20xULN
AST	>3xULN; >5xULN; >8xULN >10xULN; >20xULN
ALT or AST	>3xULN; >5xULN; >8xULN >10xULN; >20xULN
TBL	>1.5xULN, >2xULN, >3xULN,
ALP	>2xULN, >3xULN. >5xULN
ALT or AST &	ALT or AST>3xULN & TBL >2xULN;
TBL	ALT or AST >5xULN & TBL >2xULN;
	ALT or AST >8xULN & TBL >2xULN;

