2.8.4.2 Vital signs

Analysis in vital sign measurement using descriptive summary statistics for the change from baseline for each post-baseline visit will be performed. These descriptive summaries will be presented by vital sign and treatment group. Change from baseline will only be summarized for subjects with both baseline and post-baseline values and will be calculated as:

change from baseline = post-baseline value – baseline value

The number and percentage of subjects with newly occurring notable vital signs will be

presented. Clinically notable vital signs are provided in the table below

Table 2.8-4 Criteria for notable vital sign abnormalities

Vital sign (unit)	Notable abnormalities
Systolic blood pressure (mmHg)	>= 140 mmHg or < 90 mmHg
Diastolic blood pressure (mmHg)	>=90 mmHg or <60 mmHg
Pulse (bpm)	> 100 bpm or <60 bpm

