	 Female sterilization (have had surgical bilateral oophorectomy with or without hysterectomy) or tubal ligation at least six weeks before taking study treatment. In case of oophorectomy alone, only when the reproductive status of the woman has been confirmed by follow up hormone level assessment Male sterilization (at least 6 months prior to screening). For female patients on the study, the vasectomized male partner should be the only partner for that patients 		
	 Barrier methods of contraception: Condom or Occlusive cap (diaphragm or cervical/vault caps) with spermicidal foam/gel/film/cream/vaginal suppository Use of oral_injected or implanted hormonal 		
	methods of contraception or other forms of hormonal contraception that have comparable efficacy (failure rate <1%), for example hormone vaginal ring or transdermal hormone contraception		
	 Placement of an intrauterine device or intrauterine system In case of use of oral contraception, women should have been stable on the same pill for a minimum of 3 months before taking study 		
	treatment. Women are considered post-menopausal and not of child bearing potential if they have had 12 months of natural (spontaneous) amenorrhea with an appropriate clinical profile (e.g., age appropriate, history of vasomotor symptoms) or six months of spontaneous amenorrhea as defined by		
	Central Lab FSH and/or estradiol levels		
EXCL12	Subjects with active ongoing inflammatory diseases other than PsA that might confound the evaluation of the benefit of Secukinumab therapy, should not be included in the study.	1	Include in everything
EXCL13	Subjects with underlying metabolic, hematologic, renal, hepatic, pulmonary, neurologic, endocrine, cardiac, infectious or	1	Include in everything

	gastrointestinal conditions, which in the opinion of the investigator immunocompromises the patient and/or places the patient at unacceptable risk for participation in an immunomodulatory therapy should not be included in the study.		
EXCL14	Subjects with significant medical problems or diseases, including but not limited to the following: uncontrolled hypertension (≥ 160/95 mmHg), congestive heart failure (New York Heart Association status of class III or IV), uncontrolled diabetes, should be excluded from the study.	1	Include in everything

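### SAP 2.8.4.2 counts only newly occurring notable blood pressure at a single 140/90 tier, so further rises in patients admitted at 140-159 systolic or 90-94 diastolic do not show in that table

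*Protocol*

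**What the plan says.** The counting rule is in SAP 2.8.4.2: "The number and percentage of subjects with newly occurring notable vital signs will be" presented. The term newly occurring is not defined there. Table 2.8-4 sets the systolic limits at ">= 140 mmHg or < 90 mmHg" and the diastolic limits, in a separate row, at ">=90 mmHg or <60 mmHg". There is no higher tier.

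The entry limit is higher. Exclusion criterion 14 (Protocol 4.2) bars "Significant medical problems or diseases, including but not limited to the following: uncontrolled hypertension" at 160/95 or above. SAP 5.5 repeats it under EXCL14 as "uncontrolled hypertension (≥ 160/95 mmHg".

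The other planned vital-sign output, also in SAP 2.8.4.2, is descriptive statistics for change from baseline at each post-baseline visit, by treatment group.

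Laboratory data are handled differently in SAP 2.8.3: "Newly occurring or worsening liver enzyme abnormalities will also be summarized", at several tiers (Table 2.8-3). There are also shift tables, including shifts to the most extreme value.

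Protocol 6.5.2 refers the reader elsewhere for the limits: "Clinically notable vital signs are defined in" Appendix 1. That appendix names vital signs in its title, but opens with "The following criteria will be used to define expanded limits and notable abnormalities of key laboratory tests", and in the available text it lists laboratory limits only.

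**The concern.** The threshold for a notable value lies below the threshold for entry, so a band of eligible patients is already notable before the first dose. A count restricted to new occurrences cannot register a further rise in that band. These are the patients closest to clearly high pressures. Vital signs are named in the safety objective (Protocol 2.2), and the trial compares two doses with placebo. If pressure rose on treatment in patients with raised entry values, the categorical table would not show it. Patients who are counted appear only as 140 or above, so the table does not separate 142 from 185.

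**Working it through.** **Step 1: the rule, with no assumptions.** Take newly occurring to mean not meeting the criterion at baseline, where baseline is the last value before first dose (SAP 2.1.1).

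- Baseline 130, later 165: counted, reported as 140 or above.
- Baseline 150/85, later 185/110: not counted in the systolic row, counted in the diastolic row.
- Baseline 150/92, later 185/110: counted in neither row.

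**Step 2: how many patients this could affect.** The plan states no figure to reproduce and gives no blood pressure distribution, so everything in this step is assumed.

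Model for systolic pressure: patient level T is normal with mean m and variance s² - w². Baseline is B = T + e0, kept if 90 ≤ B < 160. Visit values are Vk = T + d + ek. Each e is normal with SD w, and d is an on-treatment shift. The quantity wanted is

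share missed = P(B ≥ 140 given that max Vk ≥ 160).

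Assumed ranges: m 120 to 140, s 14 or 17, w 7 or 10, d 0 or +10 mmHg. The visit numbers come from Protocol Table 6-1: 7 post-baseline visits to Week 16 (Weeks 1, 2, 3, 4, 8, 12, 16) and 16 to Week 52. Selected results:

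| m | s | w | d | visits | baseline 140-159 | reach ≥160 | of these, missed by systolic row |
|---|---|---|---|---|---|---|---|
| 120 | 14 | 10 | +10 | 16 | 7.5% | 13.6% | 28% |
| 125 | 14 | 10 | +10 | 7 | 13.9% | 15.9% | 40% |
| 130 | 14 | 10 | 0 | 7 | 22.5% | 7.3% | 61% |
| 130 | 17 | 7 | 0 | 7 | 25.2% | 7.1% | 92% |
| 140 | 17 | 7 | 0 | 7 | 43.1% | 16.5% | 94% |

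The first and last rows are the extremes of the whole grid, so the range is 28% to 94%. For scale, the third row in an arm of 100 gives 100 × 0.073 = 7.3 patients reaching 160, of whom 7.3 × 0.609 = 4.4 are missed.

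**Step 3: give credit for the diastolic row.** A bivariate version uses systolic SD 15, diastolic mean 79, SD 9.5, within-patient SD 6, correlation 0.6, a diastolic shift of half the systolic shift, and entry below 160 and below 95. A patient is treated as caught if diastolic pressure is below 90 at baseline and reaches 90 later. The share missed by both rows then runs from 10% (m 120, w 10, d +10, 16 visits) to 46% (m 140, w 7, d 0, 7 visits). It is below one half in every scenario.

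**Step 4: would copying the liver wording help?** With no drug effect, 7 visits and means of 125 to 135, about 61% to 79% of patients with baseline 140 or above exceed their own baseline at some visit through visit-to-visit variation alone (between-patient/visit SD pairs 12/9, 12/12 and 10/11). If any rise counted as worsening, most of the additional cases would be noise.

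**The case against.** A reader might infer that most patients who climb to 160 go uncounted. The documents do not support that. With between-patient SD 12 and visit SD 9, means of 125 to 135 give 71% to 79% with no shift and 61% to 71% with +5 mmHg. With SDs of 10 and 11, means of 125 to 130 and a +5 shift, the share falls to 43% to 50%. The answer depends on variances that the plan does not state.

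Nor is it right that these patients are never counted:

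- The separate diastolic row catches some of them.
- They are included in the change-from-baseline summaries, which report quartiles and extremes (SAP 2.1).
- SAP 2.8.1 treats a pre-existing event that increases in severity as treatment-emergent, and Protocol 7.1 makes a clinically significant test result an adverse event.
- SAP Table 2.8-1 lists crude incidence of vital-sign notables without restricting it to new ones.

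Two further inferences also fail. The plan does not say which denominator the percentage uses, so it cannot be claimed that patients already notable at baseline stay in it. The same rule applies to every arm, and no bias between arms has been shown. The row measures new notable values, so it is not a wrong estimate of how many patients reach 160.

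These points limit the size of the problem but do not remove it. Pooled change statistics do not give the number of patients with raised entry pressure who went higher, and adverse event recording depends on the investigator's judgement. The wording difference between Table 2.8-1 and 2.8.4.2 is one more reason to define the term.

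The missing Appendix 1 limits may be a loss in the available text, since the appendix title includes vital signs. That point is conditional.

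**Conclusion.** The blind spot is real and follows from the text alone, given the ordinary reading of newly occurring. A patient admitted at 140-159 systolic cannot become a new high-systolic case; the same holds for 90-94 in the diastolic row. No categorical vital-sign table shows how many patients reach the trial's own 160/95 limit. Its size is uncertain. The 28% to 94% (systolic row) and 10% to 46% (both rows) are conditional on assumed distributions and should be quoted only as ranges. This is a gap in a descriptive safety table. It touches no primary or inferential result, and other outputs cover it in part. It merits correction because the correction is specific and cheap.

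**What to change.** In SAP 2.8.4.2:

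1. Define newly occurring as not meeting the criterion at baseline.
2. Add one of the following, by treatment group:
   - a second reporting tier at systolic ≥160 and diastolic ≥95, counted when not met at baseline; or
   - a baseline-to-worst-value shift table with systolic bands <140, 140-159, ≥160 and diastolic bands <90, 90-94, ≥95.
3. Do not add an undefined worsening rule, for the reason in step 4 of the working.

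Separately, check the full Appendix 1. If it contains no vital-sign limits, reconcile Protocol 6.5.2 and Appendix 1 with SAP Table 2.8-4.

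The cost is SAP wording and one or two table rows, using blood pressure already measured at every treatment visit (Protocol Table 6-1). The small downside is somewhat more noise and regression to the mean in the counts, to be read against the placebo arm up to Week 16. These are reporting tiers only and change no clinical management.

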6.5.3 Height and weight

Height and body weight (in indoor clothing but without shoes) will be measured at scheduled study visits as indicated in [Table 6-1](#). If possible, body weight assessments should be performed using the same scale throughout the study. The Body Mass Index will be calculated programmably.

6.5.4 Electrocardiogram (ECG)

A standard 12 lead ECG will be performed as indicated in [Table 6-1](#). ECGs must be recorded after 10 minutes rest in the supine position to ensure a stable baseline. The preferred sequence of cardiovascular data collection during study visits is ECG collection first, followed by vital signs, and blood sampling. Each ECG tracing should be labeled with study number, subject initials, subject number, date and time, and filed in the study site source documents.

Clinically relevant abnormalities should be recorded on the relevant medical history/Current medical conditions eCRF page for the baseline ECG.

Clinically relevant abnormalities noted after the baseline ECG should be reported as AE ([see Section 7](#))

6.5.5 Laboratory evaluations

A central laboratory will be used for analysis of all specimens collected listed below (except urinalysis). Details on the collection, shipment of samples and reporting of results by the central laboratory are provided in the laboratory manual. For the identification of clinically notable values, see [Appendix 1](#). All patients with laboratory tests containing clinically significant abnormal values are to be followed until the values return to normal ranges or until a valid reason, other than treatment related AE, is defined.

6.5.5.1 Hematology

Hemoglobin, platelet, red blood cell (RBC), white blood cell (WBC) and differential white blood cell counts will be measured at scheduled visits.

6.5.5.2 Clinical chemistry

Serum chemistry will include glucose, urea, creatinine, total bilirubin, AST (SGOT), ALT (SGPT), GGT, alkaline phosphatase, sodium, potassium, bicarbonate, calcium, phosphorous, total protein, albumin, and uric acid.

6.5.5.3 Urinalysis

Dipsticks will be provided by the central laboratory to the sites for local urinalysis assessments. The urinalysis results for standard parameters such as protein, glucose, blood and WBCs will be recorded in the appropriate eCRF page. Follow-up of abnormal results is left to the discretion of the investigator.

6.5.6 Pregnancy and assessments of fertility

Secukinumab must not be given to pregnant women; therefore effective methods of birth control must be used for women of child-bearing potential (see exclusion criteria definitions, [Section 4.2](#)).

A serum β -hCG test will be performed in all women of child bearing potential at Screening Visit 2; and a local urine pregnancy test at the specified visits as indicated in [Table 6-1](#). A positive urine pregnancy test requires immediate interruption of study treatment until serum β -hCG is performed and found to be negative. If positive, the subject must be discontinued from the trial.

6.5.7 Tolerability of secukinumab

Tolerability will be assessed by adverse events, laboratory values and injection site reaction.

6.5.8 Additional parameters

Blood will be obtained at the first screening visit (Visit 1) for anti-CCP antibodies and the Rheumatoid Factor (RF).

6.5.9 Appropriateness of safety measurements

The safety measures used in this study are reliable and relevant standard measures for a biologic in PsA. A chest X-ray at screening (or within 3 months prior to screening) is performed to rule out the presence of a pulmonary malignancy or infectious process, in particular tuberculosis. The radiation exposure that results from the chest X-ray safety measurements are estimated to be far below 1 mS. Effective radiation doses under 3 mS (300 mrem), are considered to be minimal risk. Therefore, the radiation exposure in this study involves minimal risk and is necessary to ensure reliable safety measures before the treatment with a biologic.

The safety assessments selected are standard and adequate for this indication/subject population.

7 Safety monitoring

7.1 Adverse events

An adverse event (AE) is any untoward medical occurrence (i.e., any unfavorable and unintended sign [including abnormal laboratory findings], symptom or disease) in a subject or clinical investigation subject *after providing written informed consent* for participation in the study. Therefore, an AE may or may not be temporally or causally associated with the use of a medicinal (investigational) product.

The occurrence of adverse events should be sought by non-directive questioning of the patient at each visit during the study. Adverse events also may be detected when they are volunteered by the patient during or between visits or through physical examination, laboratory test, or other assessments.

Abnormal laboratory values or test results constitute adverse events only if they fulfill at least one of the following criteria:

- they induce clinical signs or symptoms
- they are considered clinically significant
- they require therapy

Clinically significant abnormal laboratory values or test results should be identified through a review of values outside of normal ranges/clinically notable ranges, significant changes from baseline or the previous visit, or values which are considered to be non-typical in patient with underlying disease. Investigators have the responsibility for managing the safety of individual patient and identifying adverse events. Alert ranges for labs and other test abnormalities are included in Appendix 1.

Adverse events should be recorded in the Adverse Events CRF under the signs, symptoms or diagnosis associated with them, accompanied by the following information.

- the severity grade
 - mild: usually transient in nature and generally not interfering with normal activities
 - moderate: sufficiently discomforting to interfere with normal activities
 - severe: prevents normal activities
- relationship to the study treatment (no/yes)
- duration (start and end dates) or if the event is ongoing an outcome of not recovered/not resolved should be reported.
- whether it constitutes a serious adverse event (SAE - See [Section 7.2](#) for definition of SAE)
- action taken regarding study treatment
- All adverse events should be treated appropriately. Treatment may include one or more of the following:
 - no action taken (i.e. further observation only)
 - study treatment temporarily interrupted
 - study treatment permanently discontinued due to this adverse event
 - concomitant medication given
 - non-drug therapy given
 - patient hospitalized/patient's hospitalization prolonged
- outcome (not recovered/not resolved; recovered/resolved; recovered/resolved with sequelae; fatal or unknown)

Once an adverse event is detected, it should be followed until its resolution or until it is judged to be permanent, and assessment should be made at each visit (or more frequently, if necessary) of any changes in severity, the suspected relationship to the study drug, the interventions required to treat it, and the outcome.

Information about common side effects already known about the investigational drug can be found in the Investigator Brochure (IB) or will be communicated between IB updates in the form of Investigator Notifications. This information will be included in the patient informed consent and should be discussed with the patient during the study as needed.

The investigator should also instruct each patient to report any new adverse event (beyond the protocol observation period) that the patient, or the patient's personal physician, believes might reasonably be related to study treatment. This information should be recorded in the investigator's source documents. However, if the AE meets the criteria of an SAE, it must be reported to Novartis.

